4 GENERAL STATISTICAL METHODS

4.1 Analysis Sets

The analysis set for the Co-Primary Endpoints analysis includes implanted subjects with a completed 6-month visit, i.e. for subjects who withdrawn consent/ missing before 6 month time window will be excluded from the implanted analysis set. The analysis set for the other analyses will be the "intent-to-treat" analysis set, including all implanted or attempted subjects.

Roll-in patients' data will be evaluated separately from the data of those patients enrolled after the Roll-in patients.

Intention-to-Treat (ITT) subjects are included in primary analysis for primary safety and efficacy endpoints as well as secondary endpoints and other endpoints. In addition, Implant subjects alone will be evaluated as needed as reference.

ITT: A subject who signs informed consent and regardless of the study device implanted or not, being enrolled into the study.

IMPLANT and ATTEMPT subjects are included in ITT.

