3 ENDPOINT ANALYSIS

If and only if the both of primary safety and efficacy endpoints are met Performance Targets (of safety based 10%, of efficacy based 94%), we say that the study objectives are met. So, no overall significant level adjustments are employed. Endpoint 2 is medically observed (no Performance Target).

Roll-in patients' data will be evaluated separately from the data of those patients enrolled after the Roll-in patients and will not be included in the endpoint analysis.

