3.1 Primary Safety Endpoint (Endpoint 1)

Primary safety endpoint is the occurrence of one of the following events between the time of implant and within 7 days following the procedure or by hospital discharge, whichever is later:

all-cause death, ischemic stroke, systemic embolism, or device- or procedure-related events requiring open cardiac surgery or major endovascular intervention such as pseudoaneurysm repair, AV fistula repair, or other major endovascular repair.

Percutaneous catheter drainage of pericardial effusions, snaring of an embolized device, thrombin injection to treat femoral pseudoaneurysm and nonsurgical treatments of access site complications are excluded from this endpoint.

Similarities of this study results will be evaluated with foreign pivotal study results.

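### SAP section 4.1 states two incompatible primary analysis sets for the co-primary endpoints, and one of them can drop the subjects whose events Endpoint 1 is meant to count

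*SAP*

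**What the plan says.** Section 4.1 of the SAP assigns the co-primary endpoints twice.

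- Paragraph 1: "The analysis set for the Co-Primary Endpoints analysis includes implanted subjects with a completed 6-month visit". It explains that "for subjects who withdrawn consent/ missing before 6 month time window will be excluded from the implanted analysis set", and continues: "The analysis set for the other analyses will be the" ITT set, described there as everyone implanted or attempted.
- Paragraph 3: "Intention-to-Treat (ITT) subjects are included in primary analysis for primary safety and efficacy endpoints", and also secondary and other endpoints. It adds: "In addition, Implant subjects alone will be evaluated as needed as reference".

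The section then defines ITT again, this time as any subject who consents and is enrolled, whether or not a device is implanted, and places both IMPLANT and ATTEMPT subjects in it.

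Section 3.1 defines Endpoint 1 as death from any cause, ischemic stroke, systemic embolism, or "device- or procedure-related events requiring open cardiac surgery or major endovascular intervention", occurring "between the time of implant and within 7 days following the procedure or by hospital discharge, whichever is later". Section 3 makes success conditional on Endpoints 1 and 3 together: "If and only if the both of primary safety and efficacy endpoints are met Performance Targets". Endpoint 2 has no target. Section 5.6 runs the tipping-point analysis on ITT. Section 7.3.4 counts closures among subjects with imaging but gives as denominator an at-risk group that it does not define.

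**The concern.** The two paragraphs cannot both define the primary analysis of the same endpoints. Paragraph 1 is a specific rule written for exactly these endpoints, so a programmer could follow it in good faith.

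It suits Endpoint 1 badly. A 7-day safety endpoint does not need a 6-month visit to be observed, and membership of the set depends on what happened during and after the procedure. A subject whose attempt fails and ends in open cardiac surgery is not implanted, so the subject leaves both numerator and denominator. An implanted subject who dies in the first week cannot complete a 6-month visit. The explanatory clause names only withdrawn and missing subjects, so it does not say whether that death is kept.

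At stake are the pass/fail result on safety, the safety rate that will be set beside the foreign pivotal results, and whether the set is fixed before the data are seen.

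**Working it through.** **1. The plan's own figures.** Inputs from the SAP (sections 1, 3.1.2, 3.2.2): N = 40, expected Endpoint 1 rate 2.2%, target below 10.0%, expected Endpoint 3 rate 99.3%, target above 94.0%, 10% attrition to the 6-month TEE.

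- Endpoint 1: 3/40 = 7.5% passes and 4/40 = 10.0% does not. P(X ≤ 3 | 40, 0.022) = 0.989, which meets the stated 95%.
- Endpoint 3: 40 × 0.90 = 36 evaluable. 34/36 = 94.4% passes and 33/36 = 91.7% does not, so 2 non-closures are allowed, as section 3.2.2 says. P(X ≤ 2 | 36, 0.007) = 0.998.

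The sample-size figures therefore hold. The defect is in the analysis set.

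**2. The two rules side by side, for Endpoint 1.**

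| Subject | Paragraph 1 | Paragraph 3 |
|---|---|---|
| Implanted, 6-month visit completed | in | in |
| Failed attempt, open surgery | out | in |
| Failed attempt, no event | out | in |
| Implanted, dies in the first week | out by the visit condition; explanatory clause silent | in |
| Implanted, withdrawn or missing before the 6-month window | out | in |

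**3. One subject at the margin (illustrative counts).** Take three events among implanted completers and one failed attempt ending in surgery. ITT gives 4/40 = 10.0%, target missed. Paragraph 1 gives 3/39 = 7.7%, target met.

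**4. How often the two rules disagree.** Let X ~ Bin(40, p) be the events. Each event subject is excluded with probability f, so L ~ Bin(X, f) are lost. The target is met if (X − L)/(40 − L) < 0.10. The SAP gives no value for f, so 25% and 50% are assumptions. The 4.4% rate is the SAP's own upper bound for the pivotal-study rate.

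| True rate | Target met, f = 0 | f = 25% | f = 50% | Difference from f = 0 |
|---|---|---|---|---|
| 2.2% | 98.9% | 99.6% | 99.9% | 0.7 or 1.0 points |
| 4.4% | 90.2% | 95.8% | 98.9% | 5.6 or 8.7 points |

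Losing event subjects can only turn a miss into a pass here, so each difference is also the share of trials in which the two rules give different results. At 2.2%, the chance that at least one event subject is lost is 1 − (1 − 0.022f)^40, which is 20% or 36%.

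**5. Direction of the bias.** Paragraph 1 also removes subjects without events, which pushes the rate up. Expected reported rate at a true 2.2%, with the 10% losses assumed by analogy with the TEE attrition:

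| Event subjects lost | Other subjects lost | Expected rate |
|---|---|---|
| 25% or 50% | 0% | 1.7% or 1.1% |
| 25% or 50% | 10% | 1.8% or 1.2% |
| 10% | 10% | 2.2% |
| 0% | 10% | 2.4% |

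The rate is biased low only when event subjects are lost more often than the others. The probabilities in step 4 hardly move when the 10% loss of other subjects is added: for f = 25%, 99.6% at 2.2% and 95.7% at 4.4%.

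**6. Endpoint 3.** Paragraph 1 points to implanted completers, paragraph 3 to ITT, section 7.3.4 to an undefined group, and the sample size to 36 evaluable TEEs. The choice matters. With 36 imaged and 2 not closed, the rate is 34/36 = 94.4%. With all 40 in the denominator it runs from 34/40 = 85.0% (missing counted as failures) to 38/40 = 95.0% (missing counted as closed). Even if all 36 are closed, the worst case is 36/40 = 90.0%, below the target.

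**The case against.** A reader might infer that the SAP gives no ranking at all. It does: paragraph 3 calls ITT primary and implanted subjects a reference, and section 5.6 follows it. This makes ITT the likelier intention. It does not remove the earlier paragraph, which says the opposite about the same endpoints.

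It can be said that Endpoint 1 may not count a failed attempt, because its window opens at implant, and that moment does not exist for a subject never implanted. Counting the event is therefore an inference. It is the natural one, since the component covers procedure-related events and the window's end is set from the procedure, but the wording should settle it.

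A reader might also infer that paragraph 1 must bias the safety rate downward. It need not: equal losses leave the rate unchanged, and losing only subjects without events raises it.

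Finally, section 5.9 requires an amended SAP before any change to the planned analyses, which limits later choice. It does not help when both rules are already in the approved text, because following either one is no change.

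**Conclusion.** The contradiction is real and should be corrected before analysis. Section 4.1 names two different primary sets for the co-primary endpoints, never withdraws the first, and describes ITT in two ways. Taken literally, paragraph 1 removes failed attempts, and possibly early deaths, from a 7-day safety endpoint on which success depends. The resulting rate is low to the extent that event subjects are excluded more often than others, which is likely because a failed procedure or a death is itself the reason for exclusion.

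The effect on the pass/fail result is small if the device performs as planned: about 0.7% or 1.0% of trials at 2.2%, rising to 5.6% or 8.7% at the 4.4% bound. These figures rest on the assumed exclusion shares of 25% and 50%. The case for correction does not depend on them. It rests on a written rule that can give the wrong result and on a set that is not fixed in advance. For Endpoint 2 only the reported rate is affected.

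**What to change.** **Endpoints 1 and 2.** In section 4.1, delete the implanted, completed-6-month-visit rule as the primary set. Make non-roll-in ITT primary, under a single definition (for example, all implanted or attempted subjects). State that early deaths and events in failed attempts count as events. Keep implanted subjects as the reference analysis. Reword the opening of the Endpoint 1 window, in sections 1 and 3.1, so that it covers attempted procedures.

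**Endpoint 3.** Replace the undefined denominator in section 7.3.4 with one named group that agrees with section 4.1 and the sample-size basis. Subjects with an evaluable 6-month core-lab TEE (36 expected, 2 non-closures allowed) is one option. Say how failed implants are treated, because section 3.2.2 allows for two patients without effective closure whatever the reason. Report the section 5.6 worst-case analysis in ITT as supportive. It should not decide success, since it falls below 94.0% at the planned attrition.

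**Cost.** SAP wording, plus a check that the protocol's Endpoint 1 window agrees. No added subjects or data. The reported safety rate may be slightly less favourable.

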4.2 Control of Systematic Error/Bias

Selection of subjects for enrollment will be made from the Investigator's usual subject load. All subjects meeting the eligibility criteria and having signed the ICF will be eligible for enrollment in the study. To control for the potential bias that could be introduced via sponsor classification of adverse events, a Clinical Events Committee (CEC) will adjudicate important endpoints and relevant adverse events.

4.3 Number of Subjects per Investigative Site

To avoid any center effect and bias, one center will not be authorized to enroll more than 20% of the 40 subjects (n = 8) per this protocol. Further enrollment will require advance agreement from sponsor.

5 ADDITIONAL DATA ANALYSES

5.1 Other Endpoints/Measurements

Baseline and other results (include other primary and secondary endpoints) will be analyzed descriptively with continuous variables (mean, standard deviation, number of patients, minimum, maximum, etc) and discrete values (frequency table and percentage). Similarities of this study results will be evaluated with foreign pivotal study results if necessary.

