all-cause death, ischemic stroke, systemic embolism, or device- or procedure- related events requiring open cardiac surgery or major endovascular intervention such as pseudoaneurysm repair, AV fistula repair, or other major endovascular repair.

Percutaneous catheter drainage of pericardial effusions, snaring of an embolized device, thrombin injection to treat femoral pseudoaneurysm and nonsurgical treatments of access site complications are excluded from this endpoint.

2. The occurrence of composite events* including stroke (all/ ischemic/ hemorrhagic), systemic embolism and CV death (including unexplained cause) .

*All data collected up to the last patient's 6 months follow-up visit to be completed.

3. The rate of effective LAA closure* at 45 days and 6 months. Change in the rate between the two time points will also be analyzed.

*The effective LAA closure is defined as peri-device flow \leq 5mm demonstrated by TEE. TEE measurements will be assessed by independent Core Lab.

A study to confirm the safety and effectiveness of the BSJ003W in Japanese patients with non-valvular atrial fibrillation at increased risk of thromboembolism in Japanese clinical environment	
Secondary endpoints	
Safety endpoints:
 
 • The occurrence of major bleeding* at 0 – 45 days, 45 days – 6 months, 6 months – 24 months 
*Major bleeding is defined as per BARC bleeding definition type 3 or 5
 
 • Frequency of the following bleeding events at 0 – 45 days, 45 days – 6 months and 6 months – 24 months: • Clinically overt non-fatal bleeding* • All bleeding events 
*Clinically overt non-fatal bleeding is defined as per BARC bleeding definition type 2.
 
Effectiveness endpoints:
 
 • The occurrence of composite events* for effectiveness; stroke (all/ ischemic/ hemorrhagic), systemic embolism and CV death (including unexplained cause) 
*All data collected up to the last patient's 12 months and 24 months follow-up visits to be completed.
 
 • Effective LAA closure at 12-month and its time course until then. • The occurrence of ischemic stroke or systemic embolism (excluding 7 days after implanting or day after hospital discharge whichever is later) at 6 months, 12 months and 24 months.

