Additional Endpoints	
Device performance:
 
 • Technical Success defined as successful delivery and release of BSJ003W into the LAA including successful recapture and retrieval if necessary. 
Safety endpoints:
 
 • Occurrence of reportable adverse events • Occurrence of all-cause mortality 
Effectiveness endpoints:
 
 • Individual occurrence of all-cause death, ischemic stroke,

A study to confirm the safety and effectiveness of the BSJ003W in Japanese patients with non-valvular atrial fibrillation at increased risk of thromboembolism in Japanese clinical environment									
	
hemorrhagic stroke, systemic embolization, cardiovascular death (including unexplained cause) at 6-month, 12-month and 24-month.
 
 • Warfarin discontinuation rate at 45 days, 6-month and 12-month • Severity of stroke assessed by NIH Stroke Score, Modified Rankin Scale Score, and Barthel Index 
Other endpoint:
 
 • EQ-5D 								
Required Medication Therapy	
  
 Visit	Medication	
   
 Implant through 45-day visit	ASA+ Warfarin	
 
 45-day visit through 6-month visit	ASA+ Thienopyridine	
 
 Following the 6-month visit	ASA	
  
 
Warfarin therapy should be appropriately monitored and adjusted so as to achieve a therapeutic INR of 2.0- 3.0. For a subject who are 70 years old or older, a therapeutic INR of 2.0 – 2.6 is recommended considering the high risk of major bleeding. Subjects should remain on warfarin until the 45-day TEE evaluation has shown adequate seal of the LAA. If the LAA is not adequately sealed, the subjects should be on warfarin and Aspirin therapy.
	Visit	Medication	Implant through 45-day visit	ASA+ Warfarin	45-day visit through 6-month visit	ASA+ Thienopyridine	Following the 6-month visit	ASA
Visit	Medication								
Implant through 45-day visit	ASA+ Warfarin								
45-day visit through 6-month visit	ASA+ Thienopyridine								

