Following the 6-month visit	ASA								
Follow-up Schedule	
Study procedures and follow-up visits will occur as follows:
 
 • Informed consent • Screening • BSJ003W Implant • 45-day Follow-up (45 ± 15 days) • 6-Month Follow-up (180 ± 15 days) • 12-Month Follow-up (365 ± 30 days) • 18-Month Follow-up (540 ± 60 days) • 24-Month Follow-up (730 ± 60 days) 								
Study Duration	
The duration of the study is expected to last approximately 3 years. The duration of individual subject participation is expected to last approximately 2 years.
								

A study to confirm the safety and effectiveness of the BSJ003W in Japanese patients with non-valvular atrial fibrillation at increased risk of thromboembolism in Japanese clinical environment	
Key Inclusion Criteria	
 1. The subject is Japanese, over 20 years old and provides written informed consent to participate in the trial 2. The subject has documented paroxysmal, persistent or permanent non-valvular atrial fibrillation 3. The subject has a calculated CHA₂DS₂-VASc score of 2 or greater and is recommended for long-term oral anti-coagulation therapy 4. The subject is deemed by their physicians to be suitable for anticoagulant therapy and have an appropriate rationale to seek a non-pharmacologic alternative to warfarin 5. The subject is eligible to come off warfarin therapy if the LAA is sealed (i.e. the subject has no other conditions that would require warfarin therapy).

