5.6 Sensitivity Analysis for Missing outcome data

Sensitivity analyses for the binary primary effectiveness and/or safety endpoints assessment will be conducted to assess the impact of missing data on the result's robustness, if necessary. In addition to the use of the worst-case analysis, the tipping point analysis will be performed for the ITT analysis set to consider all combinations of present/absent for all subjects with missing primary outcome. No imputation will be made to the other endpoints/parameters unless specified.

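### Section 5.1 reports stroke, embolism and death by 6, 12 and 24 months as plain percentages, with no rule for subjects lost before the horizon

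*SAP*

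**What the plan says.** Two groups of endpoints in the Protocol Summary (section 1) carry a time horizon for each subject:

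- Secondary effectiveness: ischemic stroke or systemic embolism after the peri-procedural period, "whichever is later) at 6 months, 12 months and 24 months".
- Additional effectiveness: all-cause death, ischemic stroke, hemorrhagic stroke, systemic embolism and CV death, each taken singly. The list ends "cardiovascular death (including unexplained cause) at 6-month, 12-month and 24-month".

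Section 5.1 fixes the method: "Baseline and other results (include other primary and secondary endpoints) will be analyzed descriptively". For categorical results this means "discrete values (frequency table and percentage". The same section allows comparison with the foreign pivotal study where needed.

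Section 4.1 assigns the secondary and other endpoints to the ITT set. Section 5.6 plans worst-case and tipping-point analyses for the binary primary endpoints and then says "No imputation will be made to the other endpoints/parameters unless specified". Section 7.3.4 has a denominator based on subjects at risk, but only for the LAA closure rate. The SAP does not mention Kaplan-Meier, cumulative incidence, person-time or censoring.

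**The concern.** An event rate by 24 months is a probability over a fixed span of time. A plain percentage estimates it properly only if every subject is followed to the horizon, or has the event or dies first. A subject who withdraws at month 3 without an event tells us about three months and nothing about the other twenty-one. A percentage can handle that subject in two ways:

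- Keep the subject in the denominator. The unobserved time is then counted as event-free, and the rate is biased down, which favours the device.
- Drop the subject. The observed event-free time is thrown away, and the rate is biased up.

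Section 4.1 points to the first way without saying so for lost subjects. Two analysts following the SAP could therefore report different 24-month rates from the same data. At stake is the accuracy of the late stroke, embolism and death rates, and of any comparison of them with the foreign pivotal results.

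**Working it through.** **The plan's own figures.** The SAP gives no expected rate for these endpoints, so there is nothing to reproduce on this point. Its sample-size statements are not challenged, and they do reproduce: with 40 subjects and a 2.2% rate, P(at most 3 events) = 98.9%; with 36 subjects and a 0.7% failure rate (100% − 99.3%), P(at most 2 failures) = 99.8%. Both exceed 95%.

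**Inputs**

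- Number of subjects: 40 (section 1).
- Event hazard: not in the SAP. Assumed λ = 0.05 per year, constant.
- Loss by 24 months: not in the SAP. Assumed 10% or 20%, at a constant rate δ and independent of risk.
- Horizon: T = 2 years.

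**Formulas**

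- True risk = 1 − exp(−λT)
- ITT percentage (lost counted event-free) = λ/(λ+δ) × [1 − exp(−(λ+δ)T)]
- Completers plus events (subjects lost event-free are dropped) = ITT percentage / [ITT percentage + exp(−(λ+δ)T)]

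**Results**

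True risk = 1 − exp(−0.10) = 9.52%.

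*10% loss.* δ = −ln(0.9)/2 = 0.0527, and exp(−(λ+δ)T) = 0.9048 × 0.9 = 0.8144.

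- ITT: (0.05/0.1027) × 0.1856 = 9.04%. Shortfall in 40 subjects: 40 × (0.0952 − 0.0904) = 0.19.
- Completers plus events: 0.0904/(0.0904 + 0.8144) = 9.99%.

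*20% loss.* δ = −ln(0.8)/2 = 0.1116, and exp(−(λ+δ)T) = 0.9048 × 0.8 = 0.7239.

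- ITT: (0.05/0.1616) × 0.2761 = 8.55%, to more digits 8.545%, so 8.5%. Shortfall: 40 × (0.0952 − 0.0855) = 0.39.
- Completers plus events: 0.0855/(0.0855 + 0.7239) = 10.56%. Excess: 40 × (0.1056 − 0.0952) = 0.42.

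**Range over other assumed risks** (same formulas; last column is the difference in subjects out of 40)

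| True 24-month risk | Loss | ITT | Completers plus events | Subjects (ITT / completers) |
|---|---|---|---|---|
| 5% | 10% | 4.75% | 5.26% | −0.10 / +0.10 |
| 5% | 20% | 4.49% | 5.57% | −0.21 / +0.23 |
| 10% | 10% | 9.50% | 10.50% | −0.20 / +0.20 |
| 10% | 20% | 8.98% | 11.09% | −0.41 / +0.44 |
| 20% | 10% | 19.02% | 20.90% | −0.39 / +0.36 |
| 20% | 20% | 18.00% | 21.95% | −0.80 / +0.78 |

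The relative error is roughly half the loss fraction. In 40,000 simulated trials of 40 subjects with a true risk of 10%, Kaplan-Meier averaged 10.0% at both loss levels.

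**One worked data set.** Forty subjects, deaths at months 5, 11, 17 and 23, and eight losses at months 1.5, 4.5, 7.5 and so on to 22.5. The numbers at risk at the four deaths are 38, 35, 32 and 29.

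- ITT percentage: 4/40 = 10.0%.
- Kaplan-Meier: 1 − (37/38)(34/35)(31/32)(28/29) = 11.5%.
- Lost subjects dropped: 4/32 = 12.5%.

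The exact 95% interval for 4/40 is 2.8% to 23.7%, much wider than the spread between the three answers.

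**The case against.** The other side has a good case. These endpoints are descriptive. Section 3 rests success on endpoints 1 and 3 alone, section 5.2 labels the 12- and 24-month analyses as additional, and section 5.1 plans the comparison with the pivotal study only where needed. Counts and percentages are a common choice for such endpoints in a 40-subject single-arm study, and with complete follow-up they need no correction. The error is below one subject throughout the table. All of this stands, and it limits the weight of the point. It does not remove it: the error is systematic, avoidable, and of unstated direction.

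A reader might infer more than the SAP supports in four places:

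- *That these are the trial's only long-term results.* They are not. The secondary endpoints include a composite with the note "All data collected up to the last patient's 12 months and 24 months follow-up visits to be completed", and all-cause mortality is listed separately among the additional safety endpoints.
- *That section 5.6 rules out sensitivity analysis here.* It plans none for these endpoints, which is not a prohibition. Its no-imputation rule is also compatible with censoring, which imputes nothing.
- *That the planned 10% attrition to 6 months can be projected to 24 months.* That figure concerns TEE follow-up. A subject can miss a TEE and still be followed for stroke and death.
- *That the visit window blurs the horizon.* The schedule allows "24-Month Follow-up (730 ± 60 days", but nothing says the percentages are tied to visits. Section 5.7 has rules for incomplete event onset dates, so events can be placed by date.

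**Conclusion.** The point holds as a modest one. Section 5.1 states a method for endpoints with a time horizon, and that method has no correct place for a subject lost before the horizon. The ITT set suggests a downward bias, but the SAP does not settle the denominator, so the direction is not fixed and a firm claim of bias in the device's favour would go too far.

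At an assumed true 24-month risk of 9.5%, the error is about half a percentage point under ITT at 10% loss, and about one point either way at 20% loss: under half a subject in 40. It reaches 0.8 of a subject if the true risk is 20% with 20% loss. The event rates, the losses, the constant hazards and the independence of loss and risk are all assumptions. Loss related to risk could do more harm, and censoring alone would not cure it. No performance target or success decision is affected. What is affected is how well the late rates can be compared with the foreign pivotal results.

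**What to change.** Amend section 5.1 for the stroke, systemic embolism and death endpoints at 6, 12 and 24 months:

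- Add time-to-event estimates at days 180, 365 and 730 from the procedure, with 95% confidence intervals and numbers at risk, censoring each subject at last contact.
- Use Kaplan-Meier for all-cause death.
- Use cumulative incidence for stroke, systemic embolism and CV death, with death from other causes as a competing event (for stroke and embolism, any death without a prior event).
- For late ischemic stroke or systemic embolism, count only events after the excluded peri-procedural window. Keep the horizons measured from the procedure, and let each subject enter the risk set when that window ends.
- Keep the raw counts beside the estimates, and state the denominator of every percentage.

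The cost is SAP wording, approved before the analysis as section 5.9 requires, and standard SAS procedures. The inputs are event, death and last-contact dates, which follow-up should already supply. The downside is wide intervals, and little information for components with very few events.
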